2. PROTOCOL SYNOPSIS

Name of sponsor/company: Bial - Portela & C ^a , S.A., [name], [name], Portugal	
Name of active ingredient: Zamicastat (BIA 5-1058)	
Title of study: An open-label, multicentre study to evaluate pharmacokinetics, safety and efficacy of zamicastat as adjunctive therapy in pulmonary arterial hypertension (PAH)	
Study number: BIA-51058-201	
EudraCT number: 2018-002448-10	
Coordinating investigator: [name]. med. [name], Medizinische Hochschule Hannover, Klinik für Pneumologie, [name], [name], Germany	
Study centre(s): Approximately 15 sites in 9 countries. Other sites and countries may be added as needed.	
Planned duration of the study: First patient first visit: May 2019 Last patient last visit: Nov 2020	Phase of development: II

Objectives:
 
Primary: To evaluate pharmacokinetic (PK) profile of different zamicastat doses in PAH patients to find the most promising therapeutic dosage range for the treatment of PAH disease
 
Secondary:
 
 1. To assess further PK parameters including apparent total clearance, terminal half-life and apparent volume of distribution 2. To assess the safety and tolerability of different zamicastat doses 3. To investigate the effect of different zamicastat doses on plasma dopamine β hydroxylase (DBH) activity 4. To investigate the effect of different zamicastat doses on urinary catecholamine levels (norepinephrine and dopamine) 5. To investigate the change in pulmonary haemodynamic parameters 6. To investigate the change in the 6-minute walk test (6-MWT) 7. To investigate the change in biomarkers 8. To investigate the change in cardiac structure and contractibility, assessed by echocardiography 9. To investigate the change in quality of life, assessed by SF-36v2 	

Methods / study design:
 
This is an open-label, multi-centre study in patients with PAH who are currently on stable treatment with at least one PAH medication. It is planned to evaluate the PK profile (24-hour profile and trough levels) and the safety, tolerability and efficacy of four different zamicastat doses. Each patient will start treatment with the lowest dose (50 mg zamicastat once daily) and the dose will be up-titrated to the individual highest tolerated dose (HTD) i.e. up to 200 mg zamicastat once daily.
 
A data safety monitoring board (DSMB) will periodically review the safety data and will issue a recommendation if the doses can be used as planned.
	

This study will consist of:

- A screening period, 5 to 12 days: visit V1
- Up to four dose finding periods, 14 days each:
 - Dose A: visits A1, A2 and A3
 - Dose B: visits B2 and B3
 - Dose C: visits C2 and C3
 - Dose D: visits D2 and D3
- Maintenance period, 42 days: visits MPV1, MPV2 and MPV3
- Follow-up period, 14 to 28 days: visits FU (down-titration) and FU

After confirmed eligibility, patients will initiate treatment with Dose A (50 mg zamicastat once daily) at visit A1 and will be treated with this dose level for 14 days. If Dose A was considered safe by the investigator, it will be up-titrated to Dose B (100 mg zamicastat once daily) at visit A3 and the patient will continue with this dosage for 14 days. Patients not tolerating Dose A have to be withdrawn from the study.

The up-titration is based on safety criteria, including but not limited to:

- Absence of symptomatic and/or clinically relevant orthostatic hypotension
- Systolic blood pressure (SBP) > 95 mmHg or diastolic blood pressure (DBP) > 50 mmHg
- Absence of clinically significant changes in electrocardiogram (ECG) parameters (heart rate, P-R interval, QRS duration, QT and QTc interval)
- Absence of clinically significant hypersensitivity/skin allergic reactions

After a positive safety evaluation at visit B3, the dose will be up-titrated to Dose C (150 mg zamicastat once daily) and the patient will continue on this dose level for a further 14 days. If Dose C was tolerated by the patient, it will be up-titrated at visit C3 to Dose D (200 mg zamicastat once daily) where the patient will remain for 56 days (14 days dose finding period + 42 days maintenance period).

Patients not tolerating their next dose at any time during the 14-days dose finding period will come immediately to the site or call the investigator (unscheduled visit), unless intolerance was detected during a scheduled visit and the dose will be down-titrated to the patient's previous tolerated dose. Then they will continue this treatment for 42 days during the maintenance period.

The dose which will be taken during the maintenance period will be considered as an individual HTD.

At the end of the maintenance period, the patient will have the opportunity to continue treatment in an extension study (BIA-51058-202), which will be described in a separate protocol.

Patients not tolerating the individual HTD during the maintenance period have to be withdrawn from the study. An overview of the study design is provided in Figure 1.

Number of patients (planned):

It is planned to allocate approximately 32 patients to treatment to meet the objectives of the study.

Diagnosis and main criteria for inclusion and exclusion:

Diagnosis: Pulmonary arterial hypertension (PAH)

Inclusion criteria:

For inclusion in the study, patients must fulfil all of the following criteria:

1. Male or female patients aged 18 to 75 years, inclusive.
2. Able to comprehend and willing to sign an informed consent form.
3. Diagnosis of PAH (pulmonary arterial hypertension WHO Group 1), documented by right heart catheterisation with a mean pulmonary artery pressure (mPAP) ≥ 25 mmHg, a pulmonary artery wedge pressure (PAWP) ≤ 15 mmHg and a pulmonary vascular resistance (PVR) > 3 WU [Galie N, et. al 2015; Lau EMT, et. al. 2017]:
 - a) Idiopathic, in non-vasoreactive patients
 - b) Heritable: Bone morphogenetic protein receptor type II (BMP2) mutation and other mutations, in non-vasoreactive patients
 - c) Drugs and toxin induced, in non-vasoreactive patients
 - d) Associated with connective tissue disease
 - e) Associated with simple congenital defects (atrial septal defect and/or ventricular septal defect) if closed > 12 months before inclusion.
4. The patient's last right heart catheterisation results, which were measured at the study site, must not be older than 90 days before V1 (will be considered as baseline value). Otherwise, a right heart catheterisation has to be performed as part of the study at visit A1.
5. WHO functional class II or III as judged by the investigator.
6. Stable treatment with at least one of the following approved PAH therapies for at least 90 days prior to V1: Ambrisentan, Bosentan, Macitentan, Riociguat, Selexipag, Sildenafil, Tadalafil, Epoprostenol intravenous, Iloprost inhaled or Treprostinil intravenous or subcutaneous.
7. For women: Agree not to donate ova from the time of informed consent until 30 days after the last IMP intake.
For men: Agree not to donate sperm from the time of informed consent until 90 days after the last IMP intake.

Exclusion criteria:

Patients having or being any of the following are to be excluded from the study:

1. Contraindication to zamicastat, i.e. known hypersensitivity to ingredients of zamicastat formulation.
2. Two or more consecutive measurements of SBP < 95 mmHg or DBP < 50 mmHg measured at V1.
3. Uncontrolled diabetes mellitus with HbA1c $\geq 8.5\%$ within the last three months or at screening.
4. PAH WHO Group 1 due to portal hypertension, human immunodeficiency virus (HIV) infection and schistosomiasis.
5. Any disease known to cause pulmonary hypertension other than PAH WHO Group 1.
6. Obstructive lung disease: Forced Expiratory Volume in 1 second/Forced Vital Capacity (FEV1/FVC) $< 60\%$ and FEV1 $< 60\%$ of predicted value after bronchodilator administration, as demonstrated and documented by previous spirometry data which, in

the opinion of the investigator, represent the clinical state of the patient at the time of the screening visit.

7. Restrictive lung disease: Total Lung Capacity (TLC) < 70% of predicted value, as demonstrated and documented by previous spirometry data which, in the opinion of the investigator, represent the clinical state of the patient at the time of the screening visit.
8. History of moderate to severe hepatic impairment (Child-Pugh B and C).
9. Estimated glomerular filtration rate (eGFR) < 30 mL/min/1.73 m² (measured at V1).
10. Use of the following prohibited medication or treatments during study participation: calcium channel blockers (CCBs) if used for the treatment of PAH in vasoreactive patients; drugs containing a catechol group that is metabolised by D β H e.g. rimiterole, isoprenaline, dopamine, dopexamine or dobutamide or α - and/or β -blockers.
11. Current or previous (within the past year) alcohol or substance abuse excluding caffeine or nicotine.
12. Presence of any other significant or progressive/unstable medical condition that, in the opinion of the investigator, would compromise evaluation of the study treatment or may jeopardise the patient's safety, compliance or adherence to protocol requirements.
13. For women: Pregnancy or breast-feeding. Women of childbearing potential unable or unwilling to undergo pregnancy tests and practice highly effective contraceptive measures in combination with a barrier method e.g. condom (without spermicidal foam/gel/film/cream/suppository or fat- or oil-containing lubricants), occlusive cap (diaphragm or cervical/vault caps) with spermicidal gel/film/cream/suppository from the time of informed consent until 30 days after last IMP intake. Highly effective methods for women are surgical intervention (e.g. bilateral tubal occlusion), non-hormonal implantable intrauterine device, true sexual abstinence (i.e. when this is in line with the preferred and usual lifestyle of the patient) and vasectomised partner (provided that the partner is the sole sexual partner of the patient and the partner has received medical assessment of the surgical success). Periodic abstinence (e.g. calendar, ovulation, symptothermal, post-ovulation methods), hormonal contraceptives and withdrawal are not acceptable methods of contraception.

For men: Male patients who are sexually active with a partner of childbearing potential must use, with their partner, a condom plus an approved acceptable contraceptive measure from the time of informed consent until 90 days after the last IMP intake. The following methods are acceptable methods of contraception: partner's use of combined (oestrogen and progestogen-containing) hormonal contraception associated with inhibition of ovulation (oral, intravaginal, transdermal); partner's use of progestogen-only hormonal contraception (oral, injectable/implantable, intrauterine hormone-releasing system); partner's use of implantable intrauterine device; surgical sterilisation (for example, vasectomy or bilateral tubal occlusion).
14. Previous participation in any other drug investigational study within the past 30 days (or five half-lives of investigational medicinal product [IMP] whichever is longer) prior to V1.
15. Vulnerable patients according to Section 1.61 of the ICH guideline for Good Clinical Practice E6.

Duration of treatment for the individual patient: Maximum treatment duration will depend on the individual HTD. Patients tolerating Dose D (200 mg zamicastat) will take zamicastat for up to 124 days.

Test product, dose and mode of administration: Tablets for oral administration under fed conditions containing 100 mg of zamicastat (BIA 5-1058) each. It is planned to use the following doses:

- | | |
|--------|--|
| Dose A | 50 mg zamicastat once daily (half a tablet of 100 mg) |
| Dose B | 100 mg zamicastat once daily (one tablet of 100 mg) |
| Dose C | 150 mg zamicastat once daily (one and a half tablet of 100 mg) |
| Dose D | 200 mg zamicastat once daily (two tablets of 100 mg) |

Reference therapy, dose and mode of administration: NA

Criteria for evaluation:Primary endpoint; pharmacokinetics:

The following PK parameters (24-hour profile) for zamicastat and its metabolites will be derived after a single dose of 50 mg zamicastat at visit A1 (Day 1):

1. Area under the curve 0-24h (AUC_{0-24h})
2. Maximum plasma concentration (C_{max})
3. Time until C_{max} (t_{max})

The following PK parameters (24-hour profile) for zamicastat and its metabolites will be derived at steady-state at the individual HTD and will be taken at visit MPV3.

4. Area under the curve 0-24h ($AUC_{0-24h,SS}$)
5. Maximum plasma concentration ($C_{max,SS}$)
6. Time until $C_{max,SS}$ ($t_{max,SS}$)
7. Minimum plasma concentration at the end of the dosing interval ($C_{min,SS}$)

The following PK parameter (trough level) will be derived for each dose at steady-state.

8. Minimum plasma concentration at the end of the dosing interval ($C_{min,SS}$)

Additional PK parameters may also be calculated if considered appropriate.

Secondary endpoints:Safety and tolerability endpoints:

1. Adverse events
2. Clinically relevant changes in laboratory parameters (haematology, biochemistry, coagulation, urinalysis, arterial blood gas analysis)
3. Clinically relevant changes in vital signs
4. Clinically relevant changes in ECG
5. Number of digital scars (only in patients with scleroderma)
6. Skin score (only in patients with scleroderma)

Efficacy endpoints:

Change from baseline to MPV3 in:

7. PVR, right atrial pressure (RAP), mPAP, cardiac index (CI) and mixed venous oxygen saturation (SvO_2). Further haemodynamic parameters may also be calculated if considered appropriate.
8. 6-MWT, including Borg dyspnoea score
9. Biomarker (N-terminal pro brain natriuretic peptide [NT-proBNP])
10. Echocardiogram parameters:
 - Tricuspid regurgitation, classified as absent, mild, moderate or severe
 - Right ventricular contractility, measured via tricuspid annular plane systolic excursion (TAPSE)
 - Pericardial effusion, classified as absent, traces or present
 - Right atrial area (end-systolic), right ventricular end-diastolic area
11. WHO functional class
12. Quality of life

Pharmacokinetic endpoints:

13. Apparent total clearance (CL/f)

14. Terminal half-life ($t_{1/2}$)
15. Apparent volume of distribution (V_z/f)

Pharmacodynamic endpoints:

16. Percent inhibition in plasma D β H activity (i.e. % change from baseline of D β H activity) on visits A3/B3/C3/D3, MPV1 and MPV2 (trough samples) and to visits A1 and MPV3 (24-hour profiles)
17. Maximal and minimal observed effect on D β H activity and time to occurrence of E_{max} (T_{Emax}) and E_{min} (T_{Emin}) on visit A1 (Day 1) and MPV3
18. Area under the effect-time curve (AUEC24) for % D β H inhibition on visit A1 (Day 1) and MPV3
19. Change from baseline 24-hour urinary catecholamine levels (norepinephrine and dopamine) on visits A3/B3/C3/D3 and MPV3

Additional parameters may be calculated if considered appropriate.

Statistical methods:

Analysis populations:

The **enrolled set** (ES) includes all patients who provided informed consent.

The **full analysis set** (FAS) includes all patients with at least one IMP administration.

The **pharmacokinetic analysis set** (PKS) will include all patients with an evaluable 24-hour PK profile and no major protocol deviations with an impact on PK analysis.

The **safety set** (SS) includes all patients with at least one IMP administration. The FAS and the SS are identical.

Sample size:

The clinical study BIA-51058-201 was designed to explore for the first time the pharmacokinetics, safety and efficacy of zamicastat in PAH patients in its potential therapeutic dose range (50 mg to 200 mg). Since this is an exploratory and descriptive study and no powered comparative statistical analysis is planned, study sample size was not formally calculated. Thus, it was considered that 32 patients constitute an appropriate sample size to meet the objectives of the study, considering the low prevalence of the disease and the consequent recruitment constrains.

Pharmacokinetic analysis:

The primary analysis of this study will be the analysis of the PK parameters derived by non-compartmental analysis from the plasma drug concentration-time data. Actual sampling times will be used. The area under the plasma concentration-time curve from time zero to 24-hour post-dose will be calculated using the linear trapezoidal rule.

Summary statistics will be reported, as appropriate, using the geometric mean, arithmetic mean, standard deviation, coefficient of variation, median, minimum, and maximum.

PK analysis will be based on the PKS.

Pharmacodynamic analysis:

Maximum observed effect on plasma D β H activity (E_{max}), time to occurrence of E_{max} (T_{Emax}), area under the effect-time curve (AUEC24) and urinary catecholamine levels (norepinephrine and dopamine) including changes from baseline will be described using summary statistics by each dose group. Pharmacodynamic analysis will be based on the PKS.

Safety analysis:

Treatment-emergent adverse events (TEAEs) will be summarised by MedDRA primary system organ class (SOC) and preferred term (PT). TEAEs will be summarised by severity

and drug relationship. TEAEs leading to discontinuation from the study, adverse events (AEs) of special interest and serious TEAEs will be summarised separately. All AEs will be listed.

Laboratory, vital signs and ECG parameters will be described using summary statistics.

The number of digital scars and skin score in patients with scleroderma will be analysed using standard summary statistics.

All safety analyses will be based on the SS.

Efficacy analysis:

Efficacy data will be analysed exploratively. Continuous measures will be summarised using summary statistics: mean, standard deviation, median, minimum and maximum, in addition for the changes from baseline a 95% confidence interval will be provided. Categorical variables will be summarised by using frequency counts and percentages.

The scores of each SF-36v2 subscale, as well as the physical and mental component summary scores (PCS and MCS), will be described using summary statistics.

Efficacy analyses will be based on the FAS.

Interim analyses:

No interim analyses are planned in this study.

Schedule of study procedures

	Screening	Dose finding period			42-days Maintenance period			Follow-up	
Visit no.	V1	A1 ²	A2/B2/C2/D2	A3/B3/C3/D3 ⁵	MPV1 ⁵	MPV2 ⁵	MPV3 ^{2,5} / EDV ¹	Follow-up down- titration ⁷	FU ¹⁷
	Day -12 to -5	Day 1	8 days ±2 after A1/A3/B3/C3	14 days ±2 after A1/A3/B3/C3	13 days ±2 after D3/down- titration ¹⁹	27 days ±2 after D3/down- titration ¹⁹	41 days ±2 after D3/down- titration ¹⁹	14 days ±2 after MPV3/EDV	14 days ±2 after last IMP intake
on-site visit ⊗ / telephone contact ☎	⊗	⊗	☎	⊗	⊗	⊗	⊗	☎	⊗
Initiation procedures									
Informed consent	●								
Demographics	●								
Height	●								
Weight	●						●		
Medical history	●								
Prior medication	●								
Concomitant medication	●	●	●	●	●	●	●	●	●
WHO functional class	●						●		
Inclusion/exclusion criteria	●	●							
Medication									
First IMP administration		●							
Dose increase				● ³					
Dispense IMP		●		●	●	●	● ⁷		
IMP accountability				●	●	●	●		● ⁷
Pharmacokinetics/ Pharmacodynamics									
Blood withdrawal (24h profile)		● ⁴					● ^{4,8}		
Blood withdrawal (trough level)				● ¹⁴	● ¹⁴	● ¹⁴			
Blood withdrawal (DβH activity)		● ⁴		● ¹⁴	● ¹⁴	● ¹⁴	● ^{4,8}		

[figure not shown]
	Screening	Dose finding period			42-days Maintenance period			Follow-up	
Visit no.	V1	A1 ²	A2/B2/C2/D2	A3/B3/C3/D3 ⁵	MPV1 ⁵	MPV2 ⁵	MPV3 ^{2,5} / EDV ¹	Follow-up down- titration ⁷	FU ¹⁷
	Day -12 to -5	Day 1	8 days ±2 after A1/A3/B3/C3	14 days ±2 after A1/A3/B3/C3	13 days ±2 after D3/down- titration ¹⁹	27 days ±2 after D3/down- titration ¹⁹	41 days ±2 after D3/down- titration ¹⁹	14 days ±2 after MPV3/EDV	14 days ±2 after last IMP intake
on-site visit ☒ / telephone contact ☎	☒	☒	☎	☒	☒	☒	☒	☎	☒
Urinalysis (dopamine and norepinephrine levels, 24h urine collection) ¹⁵		●		●			● ⁸		
Safety									
Adverse events	●	●	●	●	●	●	●	●	●
Vital signs ¹¹ (blood pressure, heart rate, tympanic body temperature)	●	● ¹²		●	●	●	● ¹²		●
Blood withdrawal (haematology, biochemistry and coagulation)	●			●	●		●		●
Urinalysis	●			●	●		●		●
Physical examination	●			●	●	●	●		
12-lead electrocardiogram	●	● ¹⁸		●	●	●	● ¹⁸		●
Number of digital scars ¹⁰	●			●	●	●	●		
Modified Rodnan Skin Score ¹⁰	●						●		
Blood pregnancy test ⁶	●								
Urine pregnancy test ⁶		●		●	●	●	●		●
Arterial blood gas analysis ^{16,21}		●					● ⁸		
Efficacy									
SF-36v2	●						● ⁸		
6-min walk test/Borg dyspnoea score	● ¹³						● ^{8,20}		
Echocardiography	●						● ⁸		

	Screening	Dose finding period			42-days Maintenance period			Follow-up	
Visit no.	V1	A1 ²	A2/B2/C2/D2	A3/B3/C3/D3 ⁵	MPV1 ⁵	MPV2 ⁵	MPV3 ^{2,5} / EDV ¹	Follow-up down- titration ⁷	FU ¹⁷
	Day -12 to -5	Day 1	8 days ±2 after A1/A3/B3/C3	14 days ±2 after A1/A3/B3/C3	13 days ±2 after D3/down- titration ¹⁹	27 days ±2 after D3/down- titration ¹⁹	41 days ±2 after D3/down- titration ¹⁹	14 days ±2 after MPV3/EDV	14 days ±2 after last IMP intake
on-site visit ☒ / telephone contact ☎	☒	☒	☎	☒	☒	☒	☒	☎	☒
Right heart catheterisation ^{16,22}		●					● ⁸		
Blood withdrawal biomarker	●						● ⁸		

- EDV = early discontinuation visit. An EDV has to be performed within 10 days of early discontinuation. Additionally, patients who will not participate in the extension study will be contacted by phone at the time of last patient's last visit (LPLV) to document their vital status.
- Patients will be hospitalised for 24 hours.
- The dose will be increased if the previous dose was considered safe by the investigator according to safety criteria (at A3, B3 and C3).
- Blood samples for PK and PD to be taken prior to IMP intake as well as 1, 2, 4, 8, 16 and 24 hours after IMP intake (but still prior to next IMP intake).
- The patient has to be advised not to take the IMP at home on the day of A3, B3, C3, D3, MPV1, MPV2 and MPV3.
- Only in women of childbearing potential.
- Only applicable in patients taking 150 mg or 200 mg zamicastat and who will not participate in the extension study. In case a patient will discontinue the study early due to the occurrence of an AE, down-titration is not mandatory, but at the investigator's discretion.
- Not applicable at EDV.
- Visits during the Dose-finding period:
 - Dose A (50 mg zamicastat):** visits A1, A2 and A3
 - Dose B (100 mg zamicastat):** visits B2 and B3. These visits will only be performed if the patient was up-titrated to 100 mg zamicastat at A3.
 - Dose C (150 mg zamicastat):** C2 and C3. These visits will only be performed if the patient was up-titrated to 150 mg zamicastat at B3.
 - Dose D (200 mg zamicastat):** D2 and D3. These visits will only be performed if the patient was up-titrated to 200 mg zamicastat at C3.
 If the patient's next dose will not be tolerated, the patient will be asked to come to an unscheduled visit (UV) and he/she will be down-titrated to his/her previous dose.
- In scleroderma patients only.
- Blood pressure and heart rate will be measured in supine position (two measurements) and afterwards in standing position (one measurement).

12. At A1 and MPV3 blood pressure and heart rate (two measurements in supine and one measurement in standing position) will be measured before IMP intake as well as 4, 8 and 24 hours after IMP intake.
13. Two baseline tests, separated by an interval of at least 30 minutes.
14. Blood samples will be taken prior to IMP intake.
15. 24-hour urine collection will start on the day before the respective visit.
16. Right heart catheterisation and arterial blood gas analysis have to be performed before IMP intake.
17. Applicable in all patients who will not participate in the extension study as well as in patients who discontinued early.
18. At A1 and MPV3 triplicate ECGs recordings will be performed before IMP intake, 4 and 8 hours after IMP intake. At EDV only one ECG recording will be performed.
19. Down-titration can be performed at a scheduled visit or an unscheduled visit (on-site visit or telephone contact) during the dose finding period.
20. 6-MWT has to be performed after arterial blood gas analysis but before right heart catheterisation and IMP intake.
21. Arterial blood gas analysis has to be performed before right heart catheterisation.
22. Right heart catheterisation will only be performed if no results which were measured at the study site from within 90 days before V1 are available.

Figure 1: Overview of study design

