11.4.4 Right heart catheterisation

Right heart catheterisation will be performed at visit A1, unless an RHC was performed within 90 days before visit V1 at the study site and the result of the following parameters is available: PVR, right atrial pressure (RAP), mPAP, cardiac index (CI) and mixed venous oxygen saturation (SvO₂%). Additionally, an RHC will be performed at MPV3 to determine the change of haemodynamic parameters in the patients. The RHC has to be performed before IMP intake. The following haemodynamic parameters will be determined:

- Cardiac output (CO, L/min)
- Mixed venous oxygen saturation (SvO₂%)
- Pulmonary artery pressure systolic, diastolic and mean (PAPs, PAPd and mPAP, mmHg)
- Pulmonary artery wedge pressure (PAWP, mmHg)
- Right atrial pressure (RAP, mmHg)
- Transpulmonary pressure gradient (TPG, mean PAP – mean PCWP)
- Diastolic pressure gradient (DPG, diastolic PAP – mean PCWP)
- Pulmonary vascular resistance (PVR; dyn x s x cm⁻⁵)
- Systemic vascular resistance (SVR, dyn · s/cm⁵)
- Cardiac index (CI, L/min/m²)
- Pulmonary arterial compliance (PAC; SV/PP, mL/mmHg)
- Heart rate (bpm)
- Stroke volume (mL/beat)
- Stroke volume index (mL/m²)

RHC will be performed according to the standard procedures provided in the 2015 ESC/ERS Guidelines for the diagnosis and treatment of pulmonary hypertension. [8]

If data from an RHC within 90 days before visit V1 are available, which were measured at the study site, the available data points will be transcribed to the eCRF and the procedure will not be repeated at visit A1.

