### 5.5.1 Right Heart Catheterisation

Right heart catheterisation (RHC) will be performed at visit A1 and at visit MPV3 before IMP intake to determine the change of haemodynamic parameters in the patients. If available, results from a right heart catheterisation within 90 days before V1 may be used in place of the V1 measurement. The following haemodynamic parameters will be collected:

- Cardiac output (L/min) (**CO**)
- Mixed venous oxygen saturation (%) (**SvO2**)
- Pulmonary artery pressure systolic (mmHg) (**PAPs**)
- Pulmonary artery pressure diastolic (mmHg) (**PAPd**)
- Mean pulmonary artery pressure (mmHg) (**mPAP**)
- Pulmonary artery wedge pressure (mmHg) (**PAWP**)
- Right atrial pressure (mmHg) (**RAP**)
- Transpulmonary pressure gradient (mmHg) (**TPG**)
- Diastolic pressure gradient (mmHg) (**DPG**)
- Pulmonary vascular resistance (dyn\*s/cm^5) (**PVR**)
- Systemic ventricular resistance (dyn\*s/cm^5) (**SVR**)
- Cardiac index (L/min/m^2) (**CI**)
- Pulmonary arterial compliance (mL/mmHg) (**PAC, SV/PP**)
- Heart rate (bpm)
- Stroke volume (mL/beat) (**SV**)
- Stroke volume index (mL/m^2/beat) (**SVI**)

The derived parameters **mPAP**, **TPG**, **DPG**, **PVR**, **PAC**, **SV**, and **SVI** will be recalculated from other parameters using standardised formulae below.

$$mPAP = PAPd + (PAPs - PAPd)/3$$

$$TPG = mPAP - PAWP$$

$$DPG = PAPd - PAWP$$

$$PVR = (mPAP - PAWP)/CO \cdot 80$$

$$PAC = SV/(PAPs - PAPd)$$

$$SV = CO/HR \cdot 1000$$

$$SVI = CI/HR \cdot 1000$$

The recalculated parameter values will be used in summaries and listings.

The clinical significance (yes/no) of any abnormal right heart catheterisation findings will be assessed by the investigator.

**Post-DR note:** Clinical significance as assessed by the investigator will not be used for statistical analyses (see Data Review Report, Final 1.0, 10-MAR-2022). Instead, right heart catheterisation results

will be assigned a “Low”, “Normal” or “High” value according to ranges defined by Table 4. The ranges are based on the Data Validation Plan (Final 3.0, 21-JUL-2020).

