**Table 5: Right Heart Catheterisation Normal Ranges**

Parameter	Normal Range
Cardiac output (L/min) (CO)	2.5-8.0
Mixed venous oxygen saturation (%) (S v O 2 )	60-80
Pulmonary artery pressure systolic (mmHg) (PAPs)	25-80
Pulmonary artery pressure diastolic (mmHg) (PAPd)	8-16
Mean pulmonary artery pressure (mmHg) (mPAP)	≥25
Pulmonary artery wedge pressure (mmHg) (PAWP)	≤15
Right atrial pressure (mmHg) (RAP)	<14
Transpulmonary pressure gradient (mmHg) (TPG)	>12
Diastolic pressure gradient (mmHg) (DPG)	>6
Pulmonary vascular resistance (dyn*s/cm  ) (PVR)	250-1000
Systemic vascular resistance (dyn*s/cm  ) (SVR)	800-1200
Cardiac index (L/min/m  ) (CI)	>2
Pulmonary arterial compliance (mL/mmHg) (PAC; SV/PP)	0.4-3.8
Heart rate (bpm)	50-100
Stroke volume (mL/beat) (SV)	>50
Stroke volume index (mL/m  /beat) (SVI)	>30

Recalculated results will be used for applicable parameters.

The following statistical output will be provided:

Table 15.2.1.1.1 Summary of Right Heart Catheterisation Parameters by HTD – Full Analysis Set

Table 15.2.1.1.2 Summary of Right Heart Catheterization Parameters – Full Analysis Set

Table 15.2.1.1.3 Summary of Right Heart Catheterisation Parameters by HTD – Modified Full Analysis Set

Table 15.2.1.1.4 Summary of Right Heart Catheterization Parameters – Modified Full Analysis Set

The default summary statistics of RHC test results will be presented by HTD and overall at visits A1 and MPV3. The absolute change from baseline will be presented as well. For the changes from baseline a 95% confidence interval will be provided.

Table 15.2.1.1.5 Summary of Right Heart Catheterization Parameters – Modified Full Analysis Set (TAPSE Subgroups)

The default summary statistics of RHC parameters PVR, mPAP, RAP, and CI will be presented by TAPSE subgroup and overall at visits A1 and MPV3. The absolute change from baseline will be presented as well. For the changes from baseline a 95% confidence interval will be provided.

Table 15.2.1.2.1 Incidence of Right Heart Catheterisation Abnormalities – Full Analysis Set

Table 15.2.1.2.2 Incidence of Right Heart Catheterisation Abnormalities – Modified Full Analysis Set

Number and percentage of patients with abnormal values will be displayed by HTD and overall in not CS abnormal and CS abnormal categories. Percentage will be based on the number of patients at specified visit.

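### A historical baseline catheterisation can lie up to 102 days before first dose and follow as little as 0 days of stable therapy, yet the SAP pools it with A1 baselines in the haemodynamic change tables

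*Protocol*

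**What the plan says.** - Protocol, Synopsis and Section 9.2, inclusion criterion 4: the last RHC measured at the study site "must not be older than 90 days before V1 (will be considered as baseline value". Without such a result, an RHC is done at A1 before the first intake.
- Protocol, Synopsis and Section 9.2, inclusion criterion 6: "Stable treatment with at least one of the following approved PAH therapies for at least 90 days prior to V1".
- Protocol 11.4.4: where a qualifying historical RHC exists, "the available data points will be transcribed to the eCRF and the procedure will not be repeated at visit A1".
- SAP 5.5.1: "results from a right heart catheterisation within 90 days before V1 may be used in place of the V1 measurement". The schedule of procedures has no RHC at V1; the pre-treatment RHC visit is A1.
- SAP 4.7: baseline is the last non-missing value before first IMP intake, with no limit on its age or source.
- SAP 5.5.1, tables: "The default summary statistics of RHC test results will be presented by HTD and overall at visits A1 and MPV3". Change from baseline is added with a 95% confidence interval, on the FAS and mFAS, and by TAPSE subgroup for four parameters on the mFAS. No RHC table is split by source or age of the baseline.
- SAP 3.1: the mFAS excludes patients with substantial changes in PAH-approved medication, diuretics included, but only from A1 to MPV3. The PAH-approved therapy tables in SAP 5.3 also start at A1.

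**The concern.** The study has one arm, so the mean change from baseline is the only haemodynamic evidence it will give. PVR, RAP, mPAP, CI and SvO2 head the list of efficacy endpoints. Any haemodynamic change between the baseline RHC and first dose goes straight into that mean.

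With an A1 baseline that gap is nil. With a historical baseline it can be more than three months, and three things could happen in it:

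- Background therapy that had only just become stable may still be taking effect.
- Another PAH drug may be added. Criterion 6 asks for stability of at least one therapy, and the mFAS does not look back before A1.
- The disease may progress.

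The other main efficacy baselines (6-MWT, echocardiography, NT-proBNP, SF-36v2) are taken at V1, after the 90-day stable period has been served. Only the RHC baseline can fall inside that period.

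**Working it through.** **Inputs.** Oldest accepted RHC: 90 days before V1 (criterion 4). Minimum stable therapy: 90 days before V1 (criterion 6). Screening: "A screening period, 5 to 12 days: visit V1". Titration: "Up to four dose finding periods, 14 days each", each visit with a ±2-day window. MPV3: "41 days ±2 after D3/down"-titration.

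**Check that windows accumulate.** The protocol's maximum of 124 treatment days at Dose D is reproduced by 4 × (14 + 2) + (42 + 2) + (14 + 2) = 64 + 44 + 16 = 124. The windows may therefore be added across visits.

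**Stable therapy guaranteed before the baseline RHC**
- A1 RHC: 90 + 5 = 95 days at least.
- Historical RHC at the age limit: 90 − 90 = 0 days.

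**Oldest historical RHC before first dose:** 90 + 5 = 95 to 90 + 12 = 102 days, depending on the length of screening.

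**Baseline to MPV3 at a highest tolerated dose (HTD) of 200 mg**
- A1 RHC, nominal: 4 × 14 + 41 = 97 days. With windows: 4 × 12 + 39 = 87 to 4 × 16 + 43 = 107 days.
- Oldest historical RHC, nominal: 97 + 95 = 192 to 97 + 102 = 199 days. Maximum with windows: 107 + 102 = 209 days.
- Share before any zamicastat (nominal): 95/192 = 49% to 102/199 = 51%.

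**Lower HTD.** The share rises because time on drug is shorter. At HTD 50 mg, if Dose B fails 1 to 14 days after A3, A1 to MPV3 is 14 + 1 + 41 = 56 to 14 + 14 + 41 = 69 days. With the 102-day case the share is 102/158 = 65% to 102/171 = 60%.

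**Effect on the pooled mean (illustration only).** The documents give neither the share f of patients with a historical baseline, nor their mean pre-drug change d, nor the SD of change. Assume f = 0.25 to 0.75 and d = 0.25 to 0.5 SD, of either sign. The pooled mean then shifts by f × d = 0.06 to 0.375 SD. With n = 32 the 95% confidence interval has half-width 2.04/√32 = 0.36 SD. If zamicastat had no effect, that interval would exclude zero in 6% to 54% of trials instead of 5%. With n = 25 (half-width 0.41 SD) the range is 6% to 44%. The result runs from negligible to material, and the planned tables could not show which applies.

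**The case against.** **Few patients may be affected.** Residual background effect needs a patient near the minimum of criterion 6 and an RHC near the maximum age in criterion 4. Criterion 6 has no upper limit, and a patient stable for years carries no such effect. Nothing shows that a patient at both limits was enrolled. This stands, and it limits the point to a possibility.

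**The matching limits also protect.** Because both count 90 days from V1, no accepted RHC can predate the stable course of the qualifying therapy. That is true, but it does not give any minimum time on therapy before the RHC, and it says nothing about a second drug.

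**The direction is open.** A reader might infer that the bias favours zamicastat. The documents do not support that. Protocol 6.1 describes PAH as progressive, and up to 102 further days of progression before dosing would work against the drug. A reader might also suspect regression to the mean from catheterisations prompted by worsening, but no passage says why historical RHCs were done. Nor can a percentage fall in PVR be derived, because neither the size nor the time course of background effects is given.

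**Some information is already planned.** SAP 4.2 requires a baseline footnote, and Listing 16.2.3.1 shows individual RHC values. The table and listing shells were not available, so some flagging may exist there. Even so, a footnote and a listing do not separate the two baseline types in the estimate.

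**The endpoint is secondary and exploratory.** No test or decision rule depends on it, the primary endpoint is PK, and an uncontrolled change cannot be attributed firmly to zamicastat in any case. This lowers the priority but does not justify leaving an identifiable source of non-drug change unexamined.

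**Conclusion.** The point holds as a reporting gap with potential for bias. A historical baseline can follow 0 days of stable therapy against at least 95 for an A1 baseline. At HTD 200 mg it can stretch the interval to MPV3 from 87–107 days to as much as 209, about half of it before any zamicastat. The SAP text pools the two types, and the mFAS does not reach back to a historical RHC. These statements rest on the documents' own limits and visit windows.

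Whether pre-drug change actually enters the results, in which direction and by how much, cannot be determined from the documents. A reader might conclude that background therapy is certainly being credited to zamicastat; the text shows only that it may be. The change should be made before the haemodynamic tables are interpreted. It does not touch the primary PK analysis.

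**What to change.** In SAP 5.5.1:

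1. Derive three variables: baseline RHC source (A1 or historical), the interval from that RHC to A1, and the days on unchanged PAH-approved medication at the RHC date.
2. Present the overall RHC change tables (15.2.1.1.2 and 15.2.1.1.4) by baseline source as well as pooled.
3. Add a sensitivity analysis restricted to patients with an A1 baseline, or with a historical RHC done after at least 90 days on the unchanged regimen and no PAH-approved medication change between that RHC and MPV3.
4. Flag historical values wherever they appear under the A1 label, and reconcile the reference to a V1 measurement with the A1 RHC visit.

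**Cost.** SAP wording, three derived variables and a few tables, with no new patient procedure. Medication start and stop dates are already collected (SAP 5.3). The RHC date is not among the items listed in SAP 5.5.1, but the site needs it to apply the 90-day limit, so its presence in the database should be confirmed. The price is small numbers in the split and restricted tables of an exploratory secondary endpoint. For that reason the split is proposed for the overall tables only, not by HTD.
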